1.3 Schedule of Activities

Table 1-1: Schedule of study assessments – Initial Treatment Period

Protocol activity \ Visit ^{a/} Week	Screening	Initial Treatment Period							SFU ^p
Written informed consent/assent	X								
Inclusion/exclusion criteria	X	X							
Demographic data	X								
Psoriasis history	X								
Significant past medical history and concomitant diseases	X								
Physical examination ^d	X	X				X	X	X	
Weight	X	X		X		X	X	X	X
Height	X	X				X	X	X	X
Vital signs (heart rate/blood pressure/temperature) ^e	X	X		X	X	X	X	X	X
Hematology/chemistry/urine ^f	X	X ¹	X			X	X	X	X
Plasma for BKZ concentration and anti-BKZ antibodies ⁿ		X	X	X	X	X	X	X	X
Hepatitis B and C and HIV testing ^g	X								
Pregnancy testing ^h	X	X		X	X	X	X	X	X
Chest X-ray ⁱ	X								
Tuberculosis test (IGRA) ^j	X								
Tuberculosis questionnaire	X	X					X		X
BSA	X	X	X	X	X	X	X	X	X

Table 1-1: Schedule of study assessments – Initial Treatment Period

Protocol activity \ Visit ^a / Week	Screening	Initial Treatment Period							SFU ^b
PASI	X	X	X	X	X	X	X	X	X
IGA	X	X	X	X	X	X	X	X	X
CDLQI		X		X	X	X	X	X	
Scalp IGA ^k		X		X	X	X	X	X	
C-SSRS	X	X		X	X	X	X	X	X
PHQ-9	X	X		X	X	X	X	X	
Adverse events	X	X	X	X	X	X	X	X	X
Concomitant medication	X	X	X	X	X	X	X	X	X
IVRS/IWRS	X	X	X	X	X	X	X	X	X
IMP administration		X		X	X	X	X		

AE=adverse event; BSA=body surface area; BKZ=bimekizumab; CDLQI=Children's Dermatology Life Quality Index; eCRF=electronic Case Report Form; C-SSRS= Columbia Suicide Severity Rating Scale; EDV=Early Discontinuation Visit; HIV=human immunodeficiency virus; IGA=Investigator's Global Assessment; IGRA=interferon-gamma release assay; IMP=investigational medicinal product; IVRS=interactive voice response system; IWRS=interactive web response system; OLE=Open-label Extension; PASI=Psoriasis Area and Severity Index; PHQ-9=Patient Health Questionnaire 9; scalp IGA=scalp-specific Investigator's Global Assessment; SFU=safety follow up; W=week

^a Visit windows of ±3 days.

^b If participant is not eligible for the OLE Period at Week 20 or does not wish to continue into the OLE Period.

^c The EDV is only needed if the participant is not entering the OLE Period.

^d Physical examination findings (Week 0 to Week 20) that are clinically significant will be recorded as AEs.

^e Pulse, systolic/diastolic blood pressure, and temperature are to be measured prior to IMP administration and prior to any blood collection.

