^f Analyses will be performed by a central laboratory, except urine dipsticks, which will be assessed locally at the site. Participants do not have to be fasting.

^g Serum samples will be obtained for the hepatitis B and hepatitis C assessment. A plasma sample will be obtained for the HIV assessment. The HIV test results will not be recorded in the eCRF.

^h Pregnancy testing for postmenarchal female participants. Serum testing by central laboratory at Screening and urine testing locally at the site for all other time points.

Table 1-1: Schedule of study assessments – Initial Treatment Period

Protocol activity \ Visit ^a / Week	Screening	Initial Treatment Period							SFU

ⁱ If a participant has had a recent radiograph of the chest within approximately 6 months prior to Screening, this may be used in lieu of the protocol-required radiograph

^j The IGRA testing is required to be performed by the central laboratory.

^k Scalp IGA to be completed for all participants at Baseline. Post-Baseline scalp IGA will only be completed for participants with a scalp IGA score >0 at Baseline.

^l Hematology, chemistry, and urinalysis will only be performed at Baseline if, in the Investigator's opinion, there is a change in the study participant's status compared with the Screening Visit.

^m Screening must be completed, at the latest, 10 days prior to the Baseline Visit to allow time for shipping of IMP to the site.

ⁿ Should IMP administration occur, plasma for BKZ concentration and anti-BKZ antibodies collection should be performed prior to IMP administration.

Table 1-2: Schedule of study assessments – Open-label Extension Period

Protocol activity \ Week ^a	OLE Period																							
Physical examination ^d	X		X			X			X			X			X			X			X		X	X
Weight	X		X			X			X			X			X			X			X		X	X
Height	X								X													X		X
Vital signs (heart rate/blood pressure/temperature) ^e	X		X			X			X			X			X			X			X		X	X

Table 1-2: Schedule of study assessments – Open-label Extension Period

Week ^a

Protocol activity

	OLE Period																												
Hematology/chemistry/urine ^f	X		X			X			X			X			X			X			X			X			X	X	
Plasma for BKZ concentration and anti-BKZ antibodies ^l	X					X						X						X						X				X	X
Pregnancy testing ^g	X	X	X	X	X	X	X	X	X	X	X	X	X	X	X	X	X	X	X	X	X	X	X	X	X	X	X	X	X
Tuberculosis test (IGRA) ^h			X												X													X	
Tuberculosis questionnaire			X			X			X			X			X			X			X			X				X	X

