19. Participant has experienced primary failure (no response within 12 weeks) to one or more IL-17 biologic response modifier (eg, brodalumab, ixekizumab, secukinumab) OR primary failure to more than 1 biologic response modifier other than an IL-17 biologic response modifier.
- 20a. Participant has received any live (includes attenuated) vaccination within the 8 weeks prior to the Baseline Visit (eg, inactivated vaccines such as influenza and pneumococcal vaccines are allowed, but nasal influenza vaccination is not permitted). Live vaccines are not allowed during the study, including the SFU Period (20 weeks after the final dose of IMP). Administration of any other vaccine not mentioned above may be allowed following discussion with the Medical Monitor.
21. Participant has received Bacillus Calmette-Guerin vaccination within 1 year prior to IMP administration.

Prior/Concurrent clinical study experience

22. Participant has participated in another study of an IMP (and/or an investigational device) within the previous 3 months or 5 half-lives (whichever is longer) prior to the Baseline Visit, or is currently participating in another study of an IMP (and/or an investigational device).

Diagnostic assessments

23. Participant has positive human immunodeficiency virus antibody test.
24. Participant has presence of hepatitis B surface antigen or hepatitis B core antibody at Screening.
25. Participant has positive hepatitis C antibody test result at Screening or within 3 months prior to starting IMP. NOTE: Participants with positive hepatitis C antibody due to prior resolved disease can be enrolled, only if a confirmatory negative hepatitis C ribonucleic acid (RNA) test is obtained.
26. Participant has positive hepatitis C RNA test result at Screening or within 3 months prior to first dose of IMP. NOTE: Test is optional and participants with negative hepatitis C antibody test are not required to also undergo hepatitis C RNA testing.
- Participants with chronic stable hepatitis C (eg, presence of positive hepatitis C RNA test result at Screening or within 3 months prior to first dose of IMP) should generally be excluded. Participants with positive hepatitis C antibody due to prior resolved disease can be enrolled only if a confirmatory negative hepatitis C RNA test is obtained.

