8 STUDY ASSESSMENTS AND PROCEDURES

Study procedures and their timing are summarized in the Schedule of Activities ([Table 1-1](#) and [Table 1-2](#)). An unscheduled visit(s) can be conducted if necessary.

Protocol waivers or exemptions are not allowed.

Immediate safety concerns should be discussed with the Sponsor immediately upon occurrence or awareness to determine if the participant should continue or discontinue IMP.

Adherence to the study design requirements, including those specified in the Schedule of Activities, is essential and required for study conduct.

All screening evaluations must be completed and reviewed to confirm that potential participants meet all eligibility criteria. The Investigator will maintain a screening log to record details of all participants screened and to confirm eligibility or record reasons for screening failure, as applicable.

Procedures conducted as part of the participant's routine clinical management (eg, blood count) and obtained before signing of the ICF may be utilized for screening or Baseline purposes provided the procedures met the protocol-specified criteria and were performed within the time frame defined in the Schedule of Activities.

The maximum amount of blood collected from each participant over the duration of the study, including any extra assessments that may be required, will not exceed the maximum volume of blood as specified by IRB/IEC requirements. Repeat or unscheduled samples may be taken for safety reasons or for technical issues with the samples.

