8.2.3 Clinical safety laboratory assessments

See Appendix 2 (Section 10.2) for the list of clinical laboratory tests to be performed and to the Schedule of Activities for the timing and frequency.

The Investigator must review the laboratory report, document this review, and record any clinically relevant changes occurring during the study in the AE section of the eCRF. The

laboratory reports must be filed with the source documents. Clinically significant abnormal laboratory findings are those which are not associated with the underlying disease, unless judged by the Investigator to be more severe than expected for the participant's condition.

All laboratory tests with values considered clinically significantly abnormal during participation in the study or within 20 weeks after the final dose of IMP should be repeated until the values return to normal or Baseline or are no longer considered clinically significant by the Investigator or Medical Monitor.

If such values do not return to normal/Baseline within a period of time judged reasonable by the Investigator, the etiology should be identified and the Sponsor notified.

All protocol-required laboratory assessments, as defined in Appendix 2 (Section 10.2), must be conducted in accordance with the Laboratory Manual and the Schedule of Activities.

If laboratory values from non-protocol specified laboratory assessments performed at the institution's local laboratory require a change in participant management or are considered clinically significant by the Investigator (eg, SAE or AE or dose modification), then the results must be recorded in the eCRF.

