10.2 Appendix 2: Clinical laboratory tests

- The tests detailed in the table below will be performed by the central laboratory, with the exception of urine dipsticks and urine pregnancy tests, which will be performed locally at the site. Pregnancy tests may be performed at home during the OLE Period, and results from these tests need to be provided to the site personnel.
- Local laboratory results are only required in the event that the central laboratory results are not available in time for either IMP administration and/or response evaluation. If a local sample is required, it is important that the sample for central analysis is obtained at the same time. Additionally, if the local laboratory results are used to make either an IMP decision or response evaluation, the results must be entered into the eCRF.
- Protocol-specific requirements for inclusion and exclusion of participants are detailed in Section 5.1 and Section 5.2 of the protocol, respectively.
- Additional tests may be performed at any time during the study as determined necessary by the Investigator or required by local regulations.

Table 10-1: Protocol-required safety laboratory assessments

Laboratory assessments	Parameters			
Hematology	Platelet Count	RBC Indices: MCV MCH %Reticulocytes		WBC Count with Differential: Neutrophils Lymphocytes Monocytes Eosinophils Basophils
	RBC Count			
	Hemoglobin			
	Hematocrit			
Clinical Chemistry ^a	Blood Urea Nitrogen	Potassium	AST/serum glutamic-oxaloacetic transaminase	Total and direct bilirubin
	Creatinine	Sodium	ALT/serum glutamic-pyruvic transaminase	Total Protein
	Glucose (nonfasting)	Calcium	Alkaline phosphatase	
Routine Urinalysis	
 Specific gravity pH, glucose, protein, blood, ketones, bilirubin, urobilinogen, nitrite, and leukocyte esterase by dipstick Microscopic examination (if blood or protein is abnormal) 			
Other Screening Tests	
 Serum human chorionic gonadotropin (hCG) pregnancy test (as needed for women of childbearing potential) by central laboratory at Screening and urine pregnancy test locally for all assessments after Screening (or at home during the OLE Period) IGRA testing Serology (HBsAg and hepatitis C virus antibody) Plasma sample for HIV antibody assessment The results of each test must be entered into the eCRF.			

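### Criterion 24 excludes on hepatitis B surface antigen or core antibody, but the required screening serology names only the surface antigen

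*Protocol*

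**What the plan says.** Criterion 24 in Protocol Section 5.2 reads: "Participant has presence of hepatitis B surface antigen or hepatitis B core antibody at Screening". Either marker alone excludes.

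The tests that feed this criterion are described in three places:

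- **Schedule of Activities, Table 1-1.** The row is "Hepatitis B and C and HIV testing", done at Screening. Footnote g adds: "Serum samples will be obtained for the hepatitis B and hepatitis C assessment". Neither names a hepatitis B marker.
- **Appendix 2, Table 10-1, Other Screening Tests.** This is the only place that names the hepatitis screening markers: "Serology (HBsAg and hepatitis C virus antibody)". SAP Table 6-1 carries the same line.
- **Section 8.2.3.** It ties the two together: "All protocol-required laboratory assessments, as defined in Appendix 2 (Section 10.2), must be conducted in accordance with the Laboratory Manual" and the Schedule.

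A core antibody assay is named in only one other place, Table 10-3. There it is the IgM assay, requested in the work-up of a possible drug-induced liver injury, not at Screening.

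On recording, the Table 10-1 block that lists the HIV sample ends: "The results of each test must be entered into the eCRF". Footnote g says: "The HIV test results will not be recorded in the eCRF".

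**The concern.** An exclusion can be applied only if the result it depends on exists. Criterion 24 depends on two results, and the list of required tests supplies one. A site that follows the list has nothing on which to judge the second.

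This is a safety exclusion. It concerns adolescents who may receive an immunomodulator for up to 120 weeks by the protocol's own count (Section 4.1), in a study that monitors liver enzyme changes closely (Section 8.3.7). A participant enrolled against the criterion for want of a test would leave no trace. The case could not appear in the summary of important protocol deviations (SAP Section 6.1.2). A later liver work-up under Table 10-3 would have no Screening core antibody result for comparison.

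The HIV wording is a smaller and separate matter: a site cannot obey both recording instructions.

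**Working it through.** No sample size, error rate or other planned figure is involved, so the check is a comparison of texts.

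**Step 1: what the criterion excludes against what the panel detects.** Two markers give four combinations.

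| HBsAg | Core antibody | Under criterion 24 | If only the Table 10-1 panel is run |
|---|---|---|---|
| positive | positive | excluded | detected through HBsAg |
| positive | negative | excluded | detected through HBsAg |
| negative | positive | excluded | not detected |
| negative | negative | not excluded | passes |

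Criterion and panel disagree in the third row only. The gap is therefore confined to HBsAg-negative, core-antibody-positive participants.

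**Step 2: does another passage require the missing test?**

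- The Schedule row and footnote g are wide enough to include core antibody but do not name it. Table 10-1, which does name markers, leaves it out.
- Appendix 2 allows additional tests when the Investigator thinks them necessary or local rules require them. That is a permission, not a requirement.
- Appendix 2 refers the reader to Section 5.2 for eligibility. This leads back to criterion 24 and supplies no assay.
- Table 10-3 applies after a liver event.

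No passage in either document makes a core antibody test a required Screening assessment.

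**Step 3: size.** Let p be the proportion of otherwise eligible participants who are HBsAg-negative and core-antibody-positive. If only the listed panel were run, the expected number enrolled against criterion 24 among the planned 40 would be 40 × p. The documents give no value for p, nor any figure from which to bound it usefully, so the calculation stops there.

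**Step 4: the HIV results.** Table 10-1 puts the HIV antibody sample in the same block as the instruction to enter each result, with no exception. Footnote g makes the opposite statement for HIV without qualification. SAP Table 6-1 reproduces the Table 10-1 instruction. The two statements cannot both be followed.

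**The case against.** The best case for the plan is that criterion 24 governs and the table is only a list. Section 8 says: "All screening evaluations must be completed and reviewed to confirm that potential participants meet all eligibility criteria". Section 5 rules out waivers, and Appendix 2 defers to Section 5.2. A careful site would see that it needs a core antibody result and order one, as Appendix 2 allows. The Laboratory Manual, which is not among the documents, may already name the assay. Nor is Table 10-1 a full list of eligibility assays, since hepatitis C RNA is also absent from it. Criteria 13 and 15 separately exclude raised liver enzymes and known liver disease.

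Much of this stands as a limit on the conclusion. A reader might infer that core-antibody-positive adolescents will pass screening and be dosed, or that none of the approximately 58 people to be screened has the second marker tested. The documents support neither. Both inferences assume that every site runs the listed panel and nothing more.

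It does not remove the mismatch. The duty to confirm every criterion makes the missing test matter more, because the required panel cannot discharge that duty for criterion 24. The hepatitis C comparison does not help. Criterion 26 says that RNA testing is optional and follows a positive antibody test, and that the antibody result alone excludes where RNA testing is unavailable. A missing RNA result therefore leads to exclusion, whereas a missing core antibody result leads towards enrolment. Criteria 13 and 15 do not detect the antibody. If the Laboratory Manual names the assay, the protocol table still disagrees with it.

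On HIV, a reader might infer that minors' results would be exposed. That is not shown. Section 10.1.4 says that transferred data carry only the study identifier, and a positive test is exclusionary under criterion 23. What remains is a conflict of wording.

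**Conclusion.** The mismatch is real and uncorrected in the current text of both documents. One of the two markers in criterion 24 has no named, required Screening test. On the condition that only the listed panel is run, HBsAg-negative, core-antibody-positive participants could be enrolled undetected. Whether any would be depends on site practice, on the Laboratory Manual and on a prevalence the documents do not state, so no count is given. The primary pharmacokinetic endpoint and the planned analyses are not affected.

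The HIV recording instructions contradict each other and need a decision on which applies. Nothing here takes a view on whether core antibody ought to be an exclusion. The finding is only that the criterion and the required tests do not match.

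**What to change.** Reconcile criterion 24, Table 10-1, Schedule footnote g and SAP Table 6-1 so that every marker used to exclude has a named, required Screening test with a result available before randomisation. If criterion 24 stands as written, add hepatitis B core antibody to the serology line, state which assay is meant, and run it on the serum already drawn for hepatitis testing. The cost is one more central-laboratory assay and possibly a few more screen failures, with no extra visit or venepuncture. SAP Table 6-1 is a copy, so changing it keeps the documents consistent but alters no screening.

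Separately, reconcile the Table 10-1 sentence on entering results with footnote g, so that sites have one instruction for HIV. This costs only wording.

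The SAP version history links version 3.0 to database lock. If screening is already complete, the practical step is to establish from central-laboratory records whether core antibody was tested at Screening, and to say so in the study report.

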10.4 Appendix 4: Contraceptive Guidance and Collection of Pregnancy Information

Definitions

Woman of Childbearing Potential

A woman is considered fertile following menarche and until becoming post-menopausal unless permanently sterile (see below).

Women in the following categories **are not considered WOCBP**:

1. Premenarchal
2. Premenopausal female with 1 of the following:
 - Documented hysterectomy
 - Documented bilateral salpingectomy
 - Documented bilateral oophorectomy

Note: Documentation can come from the site personnel's review of the participant's medical records, medical examination, or medical history interview.

3. Postmenopausal female
 - A postmenopausal state is defined as no menses for 12 months without an alternative medical cause. A high follicle-stimulating hormone (FSH) level in the postmenopausal range may be used to confirm a postmenopausal state in women not using hormonal contraception or hormonal replacement therapy (HRT). However, in the absence of 12 months of amenorrhea, a single FSH measurement is insufficient.
 - Females on HRT and whose menopausal status is in doubt will be required to use 1 of the non-estrogen hormonal highly effective contraception methods if they wish to continue their HRT during the study. Otherwise, they must discontinue HRT to allow confirmation of postmenopausal status before study enrollment.

Contraception Guidance

Female participants

Female participants of childbearing potential are eligible to participate if they agree to use a highly effective method of contraception consistently and correctly as described below.

Highly Effective Contraceptive Methods ^a

Highly Effective Contraceptive Methods That Are User Dependent ^b

Failure rate of <1% per year when used consistently and correctly.

Combined (estrogen and progestogen containing) hormonal contraception associated with inhibition of ovulation ^c

- Oral
- Intravaginal
- Transdermal

Progestogen only hormonal contraception associated with inhibition of ovulation

- Oral
- Injectable

Highly Effective Methods That Are User Independent

Implantable progestogen only hormonal contraception associated with inhibition of ovulation

- Intrauterine device (IUD)
- Intrauterine hormone-releasing system (IUS)
- Bilateral tubal occlusion

Vasectomized partner

A vasectomized partner is a highly effective contraception method provided that the partner is the sole male sexual partner of the WOCBP and the absence of sperm has been confirmed. If not, an additional highly effective method of contraception should be used.

Sexual abstinence

Sexual abstinence is considered a highly effective method only if defined as refraining from heterosexual intercourse during the entire period of risk associated with the IMP. The reliability of sexual abstinence needs to be evaluated in relation to the duration of the study and the preferred and usual lifestyle of the participant.

^a In case of newly started contraception pills/IUDs, PI should consider the correct timing of starting/applying such methods in relation to the menstrual cycle and the manufacturing instruction as when these newly started methods would become effective.

^b Typical use failure rates may differ from those when used consistently and correctly. Use should be consistent with local regulations regarding the use of contraceptive methods for participants participating in clinical studies.

Pregnancy testing

- WOCBP should only be included after a confirmed menstrual period and a negative highly sensitive serum pregnancy test.
- Additional pregnancy testing should be performed as indicated in the Schedule of Activities (Table 1-1 and Table 1-2) and as required locally. Pregnancy tests may be performed at home during the OLE Period, and results from these tests need to be provided to the site personnel.
- Pregnancy testing will be performed whenever a menstrual cycle is missed or when pregnancy is otherwise suspected.

Male participants with partners who become pregnant

- The Investigator will attempt to collect pregnancy information on any male participant's female partner who becomes pregnant while the male participant is in this study.
- In cases where the partner of a male participant enrolled in a clinical study becomes pregnant, the Investigator or designee is asked to contact the participant to request consent/assent of the partner via the Partner Pregnancy Consent/Assent Form that has been approved by the responsible IRB/IEC and should be available in the Investigator site file. In case of questions about the consent process, the Investigator may contact the UCB/CRO contract monitor for the study. The Investigator will complete the information in the eCRF only after the partner has agreed that additional information can be captured and has provided the signed Partner Pregnancy Consent/Assent form. UCB's Patient Safety department is also the primary contact for any questions related to the data collection for the partner pregnancy, eventual birth, and follow up.
- After obtaining the necessary signed Informed Consent/Assent from the pregnant female partner (and/or parent/legal representative), the Investigator will record pregnancy information on the appropriate form and submit it to the Sponsor within 1 working day of learning of the partner's pregnancy. The female partner will also be followed to determine the outcome of the pregnancy. Information on the status of the mother and child will be forwarded to the Sponsor. Generally, the follow up will be at least 12 months after the delivery date. Any termination of the pregnancy will be reported regardless of fetal status (presence or absence of anomalies) or indication for the procedure.

Female Participants who become pregnant

- Any female participant who becomes pregnant while participating in the study will discontinue IMP and be withdrawn from the study as soon as pregnancy is known.
- The Investigator will collect pregnancy information on any female participant who becomes pregnant while participating in this study. Information will be recorded on the appropriate form and submitted to the Sponsor within 1 working day of learning of a participant's pregnancy. The participant will be followed to determine the outcome of the pregnancy. The Investigator will collect follow-up information on the participant and the neonate and the information will be forwarded to the Sponsor. Generally, the follow up will be at least 12 months after the delivery date. Any termination of pregnancy will be reported, regardless of fetal status (presence or absence of anomalies) or indication for the procedure.
- While pregnancy itself is not considered to be an AE or SAE, any pregnancy complication or elective termination of a pregnancy will be reported as an AE or SAE. A spontaneous abortion is always considered to be an SAE and will be reported as such. Any post-study pregnancy related SAE considered reasonably related to the IMP by the Investigator will be reported to the Sponsor as described in Section 8.3.5. While the Investigator is not obligated to actively seek this information in former study participants, he or she may learn of an SAE through spontaneous reporting.

